3.4.5 Subject Costs and Compensation

Patients will not be reimbursed for their inclusion in the study, nor will they be charged for experimental medications. The study will cost approximately \$20,000, due mostly to the expense of the Lupron injection. We anticipate receiving funding in the form of a grant from ASRM, the American Society for Reproductive Medicine.

3.5 Chart Review Selection

N/A

4. Study Variables

4.1 Independent Variables or Interventions

The standard of care for patients who undergo embryo transfer is to administer luteal phase hormonal support in order to prime the uterus for implantation. The supplementation generally consists of hormones in different forms that are administered parenterally, vaginally, orally, and/or transdermally. This supplementation generally continues until about the eighth week of pregnancy in fresh embryo transfers and until the 11th week in frozen cycles (patients who use frozen eggs). Our study intervention will be a one time subcutaneous injection at the time of embryo transfer. Patients will receive either a single dose of a short-acting GnRH agonist (Lupron) or a single injection of subcutaneous saline as a placebo.

4.1.1 Drug or Device Interventions

A single dose of Lupron 20IU (0.2 mL) will be injected subcutaneously. The placebo will be a 0.2 mL subcutaneous injection of normal saline.

4.2 Dependent Variables or Outcome Measures

Our primary outcome will be live birth rate per embryo transfer. The clinical pregnancy rate as well as the rate of twin gestation and OHSS (ovarian hyper-stimulation syndrome) will be secondary outcomes.

4.3 Risk of Harm

The FDA warns against using Lupron during pregnancy, due to adverse events seen in animal studies. However, these studies used continuous injections of Lupron. Moreover, Lupron use in human pregnancies has never been found to cause harm. The dosage of Lupron that will be given (1 mg) is degraded by 50% in less than 3 hours. This means that after 15 hours (5 half-lives), only about 3% of the original dose (0.03 mg) still exists in your system. Thus, the risk to the baby is minimal, if any, considering the embryo does not even implant into the uterus for three to five days after embryo transfer. Other potential risks are pain, bleeding, or infection at the site of injection.

4.4 Potential for Benefit

Studies in humans have shown that using Lupron increases pregnancy and live birth rates during IVF. The formulation and dose of Lupron used in this study is short acting and is metabolized and excreted from the body before implantation occurs.

5. Data Handling and Statistical Analysis

A computer-generated list of random numbers will be used for randomization. Patients will be randomized at the time of embryo transfer.

All databases will be de-identified. The identification key will be kept in a locked cabinet in the office of Genesis Fertility.

The study will take 2 years for recruitment and treatment, and 1 subsequent year for follow-up data collection (live birth status after treatment) and analysis.

Endpoints were listed above and are the gold standard for IVF experiments.

A univariate chi square analysis will be used to compare the two treatment groups with regard to percent of rate of live births in each group. Logistic regression will be used to compare rates in the treatment groups as a function of live transfer versus frozen embryo to determine any interaction effect due to type of transfer. Logistic regression will also be used to control for the possibility of any differences or confounding factors at baseline. A similar analysis plan will be used for the secondary outcomes.

6. Data and Safety Monitoring

Interim analyses will be performed after each 50 patients enrolled to ensure non-maleficance. Block analysis will ensure there is no bias at these interim analyses. We have a Data Safety and Monitoring Board who will be performing the block analyses.

Analysis will include assessment and statistical comparisons of clinical pregnancy rates, ongoing pregnancy rates, live birth rates, and any other complications, including hospitalizations, infections and miscarriage rate. Any significant difference in these outcomes at an interim analysis will trigger cessation of the study, and a complete report will be provided to the IRB that includes all clinical and research data collected in the study.

7. Reporting Results

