Randomization scheme will be computed via a computerized program accessible at randomization.com. Randomization will be in 22 blocks of 20 patients. There will be two separate randomizations, one for fresh embryo transfers and the other for frozen embryo cycles. Sequential cards with randomization allocation will be placed in doubly sealed, opaque envelopes. A single sheet confirming eligibility status and confirmation of the presence of the signed informed consent will be in the first envelope. The second envelope will be opened after there is confirmation that the patient is eligible and consented. This envelope will have a card stating the group the patient has been assigned to and blank spaces designated to record patient information. This card will be completed by the study staff and saved for reference purposes. The card will state the group that the patient was randomized to, date of embryo transfer, patient medical record number, name, and cycle type. There will also be a logbook to record the information and medication lot numbers.

Injections will be prepared at the time of randomization by a member of the study staff, and they will be administered by the clinical RN who will not know its contents. The clinical staff assessing and planning care of the patient (attending physicians and nurses) will not know the contents of the syringe (either Lupron 20IU or Saline).

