3.3 Sample Size Justification

Based on an alpha error of .05 and power of .80, with an absolute increase in LBR of 15% (consistent with earlier studies, and an overall LBR per transfer of 39.2% - from Society of Assisted Reproduction Technologies data) we will need to enroll 352 patients (176 in each group) to reach statistical significance. In order to account for attrition and the exclusion of patients moved to day 3 (earlier embryo transfer for poor embryo development), we will anticipate 20% dropout and plan to enroll 440 patients, 220 in each arm.

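### Fresh and frozen transfers are randomised on separate lists, but live birth is tested with a pooled chi-square; a stratified primary analysis would recover a little precision at no cost in patients

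*Combined protocol and SAP*

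**What the plan says.** - **Randomisation** (Section 3, Research Design and Methods): "There will be two separate randomizations, one for fresh embryo transfers and the other for frozen embryo cycles".
- **Main comparison** (Section 5, Data Handling and Statistical Analysis): "A univariate chi square analysis will be used to compare the two treatment groups with regard to percent of rate of live births". The plan does not call this test primary. It is, however, the only test named for the overall two-group comparison of live birth, and Section 4.2 makes live birth per transfer the primary outcome.
- **Transfer type in the analysis** (Section 5): "Logistic regression will be used to compare rates in the treatment groups as a function of live transfer versus frozen embryo". I read the word live here as fresh. The stated purpose of this model is to detect an interaction.
- **Adjusted model** (Section 5): "Logistic regression will also be used to control for the possibility of any differences or confounding factors at baseline". No covariates are listed.
- **Sample size** (Section 3.3): one reference rate, "an overall LBR per transfer of 39.2" per cent, with no figure by transfer type and no expected fresh/frozen mix.

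**The concern.** Separate lists keep the arms balanced within fresh and within frozen transfers. The difference in live birth rate between the two transfer types therefore contributes almost nothing to the difference between arms. A pooled chi-square does not know this and computes its variance as if that variation were still noise. When the two rates differ, the variance is too large, the true type I error falls below 5%, and some power is lost.

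The interaction model does not make this good. It asks whether the effect differs by transfer type, not what the overall effect is.

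A side point is that Section 5 lists three analyses of live birth without ranking them, and one of them has an open covariate list. That permits, though it does not state, a choice of covariates after the data are seen. If the three disagree, nothing says which one is the trial's result.

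**Working it through.** **1. The plan's own figure.** Section 3.3 gives the inputs: "Based on an alpha error of .05 and power of .80"; "with an absolute increase in LBR of 15" points (39.2% to 54.2%); and "we will need to enroll 352 patients (176 in each group").

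Two-sided formula, pooled variance under the null, p̄ = (.392 + .542)/2 = .467:

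n per arm = [1.960 × √(2 × .467 × .533) + 0.842 × √(.392 × .608 + .542 × .458)]² / .15²
= (1.383 + 0.587)² / .0225 ≈ 172.5, so 173 per arm or 346 in total.

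The stated 352 is within 3% of this, and 352/0.80 = 440. Approximate power at 176 per arm is 80.8%. The sample size reproduces.

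**2. Assumptions.** Because the documents give no stratum rates or mix, I assume:
- an overall control rate of 39.2% and a treated rate of 54.2%;
- a fresh share w of .5, .3 or .2;
- a fresh rate below the frozen rate by a gap of 0, 10, 20 or 30 points;
- equal arms within each stratum.

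**3. Share of outcome variance carried by the stratum.**

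s = w(1 − w) × gap² / (.392 × .608), with .392 × .608 = .2383.

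| Gap | s at 50:50 | s at 20:80 | 352 × s |
|---|---|---|---|
| 10 points | .25 × .01/.2383 = 1.1% | .16 × .01/.2383 = 0.7% | 2 to 4 patients |
| 20 points | .25 × .04/.2383 = 4.2% | .16 × .04/.2383 = 2.7% | 9 to 15 patients |
| 30 points | .25 × .09/.2383 = 9.4% | .16 × .09/.2383 = 6.0% | 21 to 33 patients |

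Using p̄ = .467 in place of the control rate gives, at 50:50, about 4, 14 and 32 patients.

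**4. Type I error of the pooled test.** Approximately 2[1 − Φ(1.960/√(1 − s))]. At 50:50 this is 4.9%, 4.5% and 3.9% for gaps of 10, 20 and 30 points. Simulated values over all splits are .050 to .051, .046 to .048 and .041 to .044. The Cochran-Mantel-Haenszel (CMH) test stays at .049 to .051.

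**5. Power at 176 per arm.** Simulation with 400,000 trials per scenario and a constant 15-point effect, chi-square against CMH:

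| Gap | 50:50 | 30:70 | 20:80 |
|---|---|---|---|
| 10 points | .8051 vs .8063 | .8053 vs .8062 | .8052 vs .8057 |
| 20 points | .8101 vs .8250 | .8071 vs .8187 | .8068 vs .8143 |
| 30 points | .8155 vs .8458 | .8138 vs .8415 | .8109 vs .8349 |

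With a common odds ratio instead, the differences (same column order) are 0.14, 0.10 and 0.06 points at a 10-point gap; 1.56, 1.36 and 0.95 at 20; and 3.11, 2.87 and 2.62 at 30. With no gap there is no difference. Across all 24 scenarios (4 gaps, 3 splits, 2 forms of effect) chi-square power is .803 to .816, so it does not fall below plan. A normal approximation at 50:50 gives similar gains: 0.3, 1.1 and 2.4 points.

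**6. Adding age (optional).** Logistic regression on treatment, transfer type and age was simulated with 20,000 trials per scenario. Assumptions: age with mean 34 and SD 4, truncated to 18–40; log-odds slope 0, −.05 or −.10 per year; gaps up to 20 points. It gains 0.2 to 2.4 points of power over the chi-square. Its type I error is .048 to .053. With no gap, age alone gives 0.8 to 0.9 points at the −.05 slope and 1.5 to 1.8 at −.10.

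**The case against.** The strongest reply is that nothing here is an error. The chi-square is valid, unbiased, simple and adequately powered, and the case is a preference between two sound tests. That stands, and it limits the weight of the point.

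Four further objections bear on its size.

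- **The gap is assumed.** Nothing in the documents supports 20 or 30 points. At 10 points the gain is negligible, and at zero there is none. This stands.
- **The number analysed may exceed 176 per arm.** Section 3 says patients moved to day 3 are not randomised, so part of the 20% attrition in Section 3.3 may fall before randomisation. At 220 per arm, the simulated loss under a constant difference is about 0.01, 0.2 to 0.6 and 1.2 to 1.7 points at gaps of 10, 20 and 30. This stands as a qualifier; 176 per arm is the plan's own evaluable number.
- **The figures assume a single final look.** Section 6 plans comparisons every 50 patients, with any significant difference ending the study. As an illustration, nine unadjusted looks with immediate outcomes give about 19% type I error; live birth is delayed, so the real figure would differ. That issue is separate and larger, and it does not remove this one.
- **The separate lists also serve the interaction analysis, and transfer type does appear in a model.** Both are true. Still, no section makes a stratified or adjusted overall comparison the main one.

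**Conclusion.** The point holds as a minor matter of efficiency and clarity. The main live-birth test does not use the stratum on which patients are randomised. The result is not biased, type I error is not inflated and the planned sample size is not undermined. At 176 per arm, the power given up runs from zero with no fresh/frozen gap to about 3 points at a 30-point gap, and less if more patients are analysed. These sizes rest on assumed stratum rates and mix, equal arms within stratum and one final analysis. The reason to act is that the change is free and settles which analysis is the trial's result, not that the loss is large.

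**What to change.** In Section 5, name one primary analysis of live birth that uses transfer type. Either would do:

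- (a) a Cochran-Mantel-Haenszel test stratified by fresh/frozen, reported with a stratified risk difference and 95% CI; or
- (b) logistic regression on treatment, transfer type and age, all fixed in advance, reported with a standardised risk difference and 95% CI. Age is optional, since it was not a randomisation stratum.

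Keep the unadjusted chi-square as a sensitivity analysis and the treatment-by-type interaction as secondary. Label any other adjusted model supportive and list its covariates before unblinding.

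The cost is a few sentences. Transfer type is known when the list is chosen (Section 3), and age is known from eligibility (Section 3.4.1). No patients or new data are required.

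### The interim rule stops the trial on any significant difference, live birth included, at eight looks with no level, direction or boundary; at .05 per look, about .08 to .19 of null trials would cross.

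*Combined protocol and SAP*

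**What the plan says.** Section 6 sets the schedule: "Interim analyses will be performed after each 50 patients enrolled to ensure non-maleficance". With 440 planned, the looks fall at 50, 100, ..., 400, so there are eight before the end. The comparisons are statistical and include the primary outcome: "Analysis will include assessment and statistical comparisons of clinical pregnancy rates, ongoing pregnancy rates, live birth rates", together with complications, hospitalizations, infections and miscarriage. The rule is "Any significant difference in these outcomes at an interim analysis will trigger cessation of the study", after which "a complete report will be provided to the IRB that includes all clinical and research data collected in the study". A data and safety monitoring board (DSMB) does the analyses, and the section adds: "Block analysis will ensure there is no bias at these interim analyses".

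Section 4.2 confirms the status of live birth: "Our primary outcome will be live birth rate per embryo transfer". Section 5 gives the final test without a level ("A univariate chi square analysis will be used to compare the two treatment groups") and the timetable ("The study will take 2 years for recruitment and treatment, and 1 subsequent year for follow-up data collection"). Section 7.3 commits to submitting all results for publication, whatever their direction. The only alpha in the document is the .05 in section 3.3, which supports 352 patients (440 with 20% dropout) for a 15-point rise from a live birth rate of 39.2%.

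**The concern.** The stated purpose of the looks is to avoid harm, but the trigger has no direction, so it also stops the trial for apparent benefit. It is mandatory and covers the primary outcome, and it gives the DSMB no threshold. Testing accumulating data repeatedly at an unadjusted level raises the chance of at least one significant result when nothing is going on. Section 3.3 makes no allowance for this. Block analysis does not help, because blocking balances allocation and does not control repeated-testing error.

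Two things are at stake. If a crossing is taken as the trial's result, the type I error exceeds the .05 on which the sample size rests. If it is not, an inactive injection can still end the trial before it has answered its question, and an effective one will usually end it early with an overstated effect.

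**Working it through.** **Inputs from the documents.** Control rate .392, effect +.15, alpha .05 (two-sided assumed), power .80, N = 352 evaluable and 440 enrolled (section 3.3); looks every 50 enrolled (section 6); 24 months of recruitment (section 5).

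**Assumptions, not in the documents.** A level of .05 at each look; uniform accrual; a transfer-to-birth lag of 9 months; where needed, a pregnancy rate of 50% with non-pregnancy known at 1 month.

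**1. The plan's own figure.** With pooled variance and mean rate (.392 + .542)/2 = .467:

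n per arm = [1.960 × √(2 × .467 × .533) + 0.842 × √(.392 × .608 + .542 × .458)]² / .15² = (1.383 + 0.587)² / .0225 ≈ 173.

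The plan has 176, which gives power of about .81. 352/0.80 = 440. The sample size reproduces, as a single-look calculation.

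**2. What is known at each look.** 440/24 = 18.3 patients per month, and 18.3 × 9 = 165 are pending at any time. If every outcome takes 9 months, the later looks have 200 − 165 = 35, then 85, 135, 185 and 235 known. When enrolment closes, 440 − 165 = 275 are known.

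**3. Null crossing rate, live birth only.** The test statistic is z = (p_A − p_B)/√[p̄(1 − p̄)(1/n_A + 1/n_B)], with a crossing if |z| > 1.96. Rates were simulated with 39.2% in both arms, permuted blocks of 20 and 40,000 to 100,000 trials per scenario. Continuity-corrected values are in brackets, since section 5 does not say which chi-square is meant.

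| Outcome timing (assumed) | Any crossing, interim or final | Interim halt |
|---|---|---|
| Immediate | .19 (.135) | .18 (.13) |
| 9-month lag for all | .17 (.12) | .15 (.095) |
| Non-pregnancies at 1 month, the rest at 9 | .12 (.08) | .10 (.06) |

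About half of the crossings favour the injection: .095 of .19 in the first row and .086 of .17 in the second. These are scenarios, not bounds; a 10-month lag for all outcomes with the uncorrected test gives about .20.

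**4. If patients enrolled at a halt are followed and tested at .05.** Under a lag, false positives fall to about .06 (.045 corrected), because the pending patients dilute the crossing. With a 9-month lag for all outcomes, only about 23% of the null halts remain significant after follow-up.

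**5. Adding clinical pregnancy as a trigger.** With an assumed rate of 45 to 60%, known 0 to 2 months after transfer, the null halt rate becomes .25 to .29 (.17 to .19 corrected).

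**6. A true 15-point effect, 9-month lag for all outcomes.** 72% of trials halt (66% corrected). The mean estimate in halted trials is about 24 points at the look and about 18 after follow-up.

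**7. Boundaries and power.** With looks at 50 to 250 known outcomes, the O'Brien-Fleming constant is 1.993 with a final analysis at 440 (final p .046) and 2.025 at 352 (final p .043). Haybittle-Peto uses p < .001 at interims; leaving its final level at .05 gives .052 overall, so about .048 is needed. Power, all at 352 evaluable: no looks .805 to .814; Haybittle-Peto .802 to .811; O'Brien-Fleming .795 to .804; the current rule with follow-up and a 9-month lag, about .76.

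**The case against.** The strongest reply is that these are safety looks by a DSMB, and that the two-sided wording is loose drafting of a harm rule. That may be the intent, but the text as written also stops for benefit. It is a good reason to offer a harm-only trigger as one repair.

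A reader might infer that the trial's type I error is simply .19, or that a halt ends all follow-up because section 6 mentions only a report to the IRB. The documents do not support either. They state no interim level. Section 5 plans a year of live-birth follow-up with no exception for a halted trial, and section 7.3 commits all data to publication. Follow-up after a halt is therefore a plausible reading, and on that reading the false-positive rate is near nominal. It is not stated for a halted trial, though, nor is it stated which result counts.

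A reader might also infer that no live-birth outcome is known at the first three looks. That is wrong. A patient who does not conceive has a final negative outcome within weeks, which is why the third row of the table is needed and why the range reaches down to about .08.

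The overstatement under a true effect is largely an interim snapshot, and shrinks to about 18 points against 15 after follow-up. The early halts remain.

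**Conclusion.** The point holds and should be fixed before the rule is used. Section 6 mandates stopping on the primary outcome, in either direction, at eight looks, with no level or boundary, in a trial sized at an unadjusted .05.

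The .08 to .19 crossing range rests on .05 per look, on assumed outcome timing, on live birth alone and on all 440 being evaluable. It is an error rate for the trial only if the crossing result stands as final. On the more favourable reading of sections 5 and 7.3, the conclusion is narrower but still material: near-nominal false positives (about .045 to .06), about .06 to .15 of null trials halted on live birth alone under a lag, more once clinical pregnancy also triggers, and about 66 to 72% of trials halted early if the assumed effect is real and all outcomes take 9 months.

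**What to change.** In sections 3.3 and 6:

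1. Choose and state one of two designs.
   - *Efficacy stopping intended:* replace the present trigger, for benefit, with a pre-specified boundary on live birth only at overall two-sided alpha .05. Haybittle-Peto (p < .001 at interims, final p about .048) is the simplest. O'Brien-Fleming on the same looks has a final p of about .046 at 440 or .043 at 352. Count looks by cohorts whose live-birth status is complete for every patient, so that early-known failures do not enter alone. Use only looks that fall before enrolment closes, about 50 to 250 under a 9-month lag; the 250 look comes when about 250 + 165 = 415 are enrolled.
   - *No efficacy stopping intended:* say that the trigger is for harm only and keep the final test at .05. False positives for benefit are then about .025.
2. State that patients enrolled at a halt are followed to delivery, and that the analysis including them is the trial's result.
3. State that clinical and ongoing pregnancy do not trigger a stop for benefit.
4. Keep harm monitoring separate, under written criteria set by the sponsor and DSMB. A symmetric O'Brien-Fleming boundary cannot serve: at 50 outcomes it needs z = 1.993 × √(440/50) ≈ 5.9.
5. Delete the claim that block analysis ensures no bias, and say whether the chi-square is continuity-corrected.

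The cost is text, DSMB agreement on the harm criteria and, with Haybittle-Peto, a final threshold of about .048. At 352 evaluable the power loss against no looks is about 0.3 points (.805 to .802), or about one point with O'Brien-Fleming. The harm-only option leaves the final threshold unchanged.

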1.1 Objectives

We hope to demonstrate a significant difference in pregnancy and live birth rates in IVF patients who receive a GnRH agonist (Lupron) prior to embryo implantation.

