1.2 Hypothesis

If a GnRH agonist is administered at the time of embryo transfer, then the success rate of pregnancy and live birth will be greater than the standard-of-care, which does not utilize this medication.

2. Background and Significance

During IVF cycles, an embryo is generally placed into the uterine cavity between 3 and 5 days after fertilization in a laboratory. For a successful pregnancy to take place, that embryo must then implant in the properly primed and staged endometrium, which subsequently must continue to develop to accommodate the growing and maturing embryo and soon-to-be fetus. This process is normally regulated by hormonal interactions between the fetal, endometrial and luteal tissue. It has been found that after embryo transfer additional support for the endometrium with progesterone improves implantation and, thus, live birth rates in IVF cycles (Van der Linden, Cochrane 2011). Recent data has shown that additional supplementation with a single administration of a GnRH agonist around the time of embryo transfer may further improve these rates (Oliveira, RepBiolEndo 2010; Van der Linden, Cochrane 2011, Ata 2008, Brigante 2013, Isik 2009, Tesarik 2006, Inamdar 2012, isikoglu 2007, Qublan 2008).

3. Research Design and Methods

This study is a randomized clinical trial. It will be a double-blinded, placebo-controlled study. On the day of embryo transfer (5-6 days after a fresh egg retrieval and on the sixth day of progesterone administration in a frozen embryo transfer cycle), patients will receive either

a single injection of 1mg of Lupron or an identical placebo injection. Patients undergoing day 3 embryo transfers will not be eligible and will not be randomized.

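### Section 6 stops the trial on any significant difference, favourable ones included, with no direction, level or boundary, so an early pregnancy gain can end it before live birth is answered with the planned power

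*Combined protocol and SAP*

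**What the plan says.** Section 6 gives the purpose and timing of the looks: "Interim analyses will be performed after each 50 patients enrolled to ensure non-maleficance". It then lists what is compared: "Analysis will include assessment and statistical comparisons of clinical pregnancy rates, ongoing pregnancy rates, live birth rates, and any other complications", with hospitalizations, infections and miscarriage named among the complications. The operative sentence is "Any significant difference in these outcomes at an interim analysis will trigger cessation of the study". On protection against error the section offers only "Block analysis will ensure there is no bias at these interim analyses" and assigns this work to the DSMB.

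Section 4.2 names one primary outcome, live birth rate per embryo transfer, and makes clinical pregnancy secondary. Section 3.3 sizes the trial on live birth alone: "Based on an alpha error of .05 and power of .80, with an absolute increase in LBR of 15" percentage points, against 39.2%, which gives 352 patients. For losses, "we will anticipate 20% dropout and plan to enroll 440 patients, 220 in each arm". Section 5 plans two years of recruitment and treatment, then one year to collect live-birth status and analyse. It does not say whether that follow-up still applies if the study stops early.

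**The concern.** The stated purpose is protection from harm, but the trigger works in both directions and leaves the DSMB no discretion. It covers outcomes that are known long before delivery. If the injection works as Section 1.2 supposes, pregnancy rates separate first, and the rule then ends the study on a secondary or unlisted outcome. The primary comparison is left with too few patients. Section 3.3 makes no allowance for this.

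The block-analysis sentence does not fill the gap, since it supplies no direction, level or boundary. The only significance level in the plan is the .05 used for sample size. Section 6 does not say that it applies at the looks, but nothing else is available to whoever has to apply the rule.

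**Working it through.** **The plan's own figure.** Inputs from Section 3.3: control 39.2%, Lupron 54.2%, alpha .05 (two-sided reproduces the stated number; one-sided gives 136 per arm), power .80. With mean rate 0.467:

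n per arm = [1.96·√(2·0.467·0.533) + 0.842·√(0.392·0.608 + 0.542·0.458)]² / 0.15² = [1.96·0.7056 + 0.842·0.6975]² / 0.0225 ≈ 173.

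The plan has 176, which gives 80.8% power. Also 352/0.8 = 440. The baseline reproduces.

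**Why an early stop is costly.** Fixed-sample power = Φ[(0.15·√n − 1.96·0.7056)/0.6975], n per arm. With everyone evaluable:

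| Total patients | Power for live birth |
|---|---|
| 50 | 18% |
| 100 | 32% |
| 150 | 45% |
| 200 | 57% |
| 352 | 81% |
| 440 | 89% |

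**Timing.** 440 patients over 24 months is 18.3 a month. If delivery falls 8.5-9 months after transfer (assumed), 8.5 × 18.3 ≈ 156 to 9 × 18.3 = 165 patients are enrolled before the first reaches the delivery window. So no patient has reached it at the looks at 50, 100 or 150; 35-44 have at 200, and 235-244 at 400 (before dropout).

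**Simulating the rule.** Assumptions, none of them given in the documents: control clinical pregnancy 44-52%; clinical pregnancy known at 1-1.5 months; uniform accrual; everyone enrolled followed to delivery; 20% random dropout; pregnancy and live-birth triggers only. From the plan: looks at 50 to 400, maximum 440, live birth 39.2% against 54.2%. Each scenario used 6,000 trials. Power means a final live-birth z above 1.96 in favour of Lupron. Without the rule it is 80-82%.

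At uncorrected two-sided .05, by pregnancy gain:

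| Pregnancy gain | Stop early | Live-birth power |
|---|---|---|
| Same ratio as live birth (17-20 points) | 90-97% | 41-59% |
| 15 points | 84-91% | 54-64% |
| 10 points | 71-83% | 65-73% |

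The first row follows from the ratio 54.2/39.2: 44% becomes 60.8% and 52% becomes 71.9%.

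By interim level, over all the gains:

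| Interim test | Stop early | Live-birth power |
|---|---|---|
| .05, uncorrected | 71-97% | 41-73% |
| .05, continuity-corrected | 63-96% | 50-77% |
| .01 | 43-90% | 61-80% |
| .001 | 17-68% | 76-82% |

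With live birth as the only trigger (.05), power is 75-77%, so most of the loss comes from the pregnancy triggers. With no treatment effect, 25-35% of trials stop at .05.

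**Adding the listed miscarriage trigger (.05).** About 92-97% of stops favour Lupron, and with no effect about 40% or more of trials stop. Hospitalizations and infections are not in these runs.

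**Sensitivity.** A separate simulation with no dropout, miscarriage also a trigger and different pregnancy rates gives 41-69% at 352 patients and 41-72% at 440. Its mildest case at 352 (pregnancy gain 10-12 points, no miscarriage trigger, outcomes known at once) gives 75-79%, against 80.8% without the rule.

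**The case against.** The strongest reply is that the numbers rest on assumptions. Section 6 gives no level, and the .05 belongs to the sample-size calculation. At .001 almost nothing is lost. The 41% end needs a pregnancy gain larger than the 15 points that Section 3.3 assumes for live birth. This stands. A reader might infer that the plan tests at .05 at each look and so has 41% power, but the documents support neither statement. What they do support is that a mandatory stop exists with nothing to keep it from being applied that way.

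The dropout figure is also uncertain. Section 3.3 counts patients moved to day 3 within its 20%, while Section 3 says "Patients undergoing day 3 embryo transfers will not be eligible and will not be randomized", so loss after randomisation may be smaller. With none, power is 88-89% without the rule and 47-82% with it at .05.

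A second reply is that stopping on pregnancy is legitimate, because Section 1.1 states: "We hope to demonstrate a significant difference in pregnancy and live birth rates in IVF patients". A pregnancy result would answer part of that objective, and whether benefit should stop the trial is for the sponsor and DSMB. That also stands. But Section 6 does not present its looks as efficacy looks, and such a stop leaves the sole primary outcome underpowered.

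Two further inferences should be avoided. It is tempting to say that no live-birth status is known at 50, 100 or 150 enrolled. That is wrong: a patient who is not pregnant has a known negative status within weeks. Only the delivery window has not been reached. Nor can one say that virtually every stop would favour Lupron, since the listed miscarriage comparison adds stops in the other direction.

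**Conclusion.** The concern holds, and Section 6 must be changed before use. The defect is in the text: a mandatory stop in either direction, on several outcomes, without level or boundary, set against a purpose of preventing harm. It needs no assumption.

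The cost is conditional on interim level, pregnancy rates, outcome lags and dropout. Read at the plan's only level, uncorrected, the rule takes live-birth power from about 80% to about 41-73% at the planned gain; a stricter level shrinks the loss, to almost none at .001. Confidence is high on the wording and moderate on the size.

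**What to change.** Reword the stopping sentence in Section 6 so that:

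- (a) pregnancy and live-birth comparisons stop the trial only when the Lupron arm is worse, at a level per look fixed in advance with the DSMB;
- (b) a favourable difference in clinical or ongoing pregnancy alone does not trigger a mandatory stop;
- (c) all patients already randomised are followed to delivery if recruitment stops.

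Triggers for complications remain a separate DSMB decision. Two example harm levels, under the same assumptions with 20% dropout (share of trials stopped):

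| One-sided level per look | Planned gain | No effect | True 10-point loss | True 15-point loss |
|---|---|---|---|---|
| .005 | at most 0.4% | 3-5% | 33-53% | 66-89% |
| .025 | 0.5-2.2% | 12-18% | 60-79% | 87-97% |

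Both leave live-birth power at 79-82%.

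If the sponsor and DSMB want an efficacy stop, base it on live birth, with an alpha-spending boundary and the matching final critical value. Time the look by patients past the delivery window, not by patients with any known status: negatives become known first, so the latter sample would be weighted towards failures. One O'Brien-Fleming-type look at half the live-birth information (z above 2.963, final 1.969), combined with the .005 harm rule, keeps power at 80-81%. By then 220 + 156 = 376 to 220 + 165 = 385 of 440 patients are enrolled, so it spares at most 55-64.

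The cost is protocol wording and agreement with the DSMB; the harm-only rule needs no extra patients or procedures. The downsides are no early stop for benefit on pregnancy alone, and a choice of harm level: the strict one misses 47-67% of true 10-point losses, and the looser one stops 12-18% of trials with no effect. Any change made to this sentence for repeated testing should be part of the same edit.
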